## 4.2 Schema

**Figure 4. Treatment schema.** Scans during the pre-study period may be accepted for baseline standard of care imaging if they have occurred within a particular timeframe in relation with C11-AMT or pembrolizumab in administration. An alternative scan to the FDG-PET coregistered with CT with IV contrast can be considered if patients had previously whole-body PET scan with non-contrast CT (alternative scan would then be CT of the chest, abdomen, and pelvis; neck, if applicable) or CT scan with IV contrast (alternative scan would be whole body PET scan). Nevertheless, FDG PET with coregistered CT scan with IV contrast (CTIVC) is the preferred method of baseline assessment of disease prior to pembrolizumab initiation. The evaluation period begins with signed informed consent and ends on the day of pembrolizumab infusion; it should not exceed 28 days. The evaluation period consists of two periods: screening period and pre-treatment period. During the screening period FDG PET with CTIVC, history and physical exam (H&P), review of inclusion/exclusion criteria, blood work, and planning for subsequent baseline studies is completed. As soon as screening is complete, the eligibility checklist is approved and signed by the treating physician. Under no circumstances is the time between checklist sign off and C11-AMT PET imaging less than or equal to 4 days. Pre-treatment period includes C11-AMT PET imaging (at least 1

bed position), fresh biopsy collection, and repeat of blood/urine tests. Up to four infusions of pembrolizumab are administered before the restaging FDG PET whole body with CTIVC scan is performed.

FDG PET coregistered with CT scan with IV contrast (CTIVC) is the preferred method of evaluation at baseline within the defined windows and at 12 weeks (or earlier, if the patient progresses). However alternative scan tests will be acceptable for the study as long as they fulfill certain criteria:

**A.** If the whole body PET scan has been performed previously, time elapsed between pre-study PET scan and baseline C11-AMT PET scan should be within 28 days. In this scenario, a baseline CT scan with IV contrast of the chest, abdomen, and pelvis (add neck, if applicable) will be performed within 28 days prior to starting pembrolizumab.

**B.** If whole body CT scan with IV contrast has been previously performed, time elapsed between the pre-study “diagnostic” CT scan with IV contrast and treatment initiation with pembrolizumab should be at most 28 days. In this case, a whole body PET scan must be performed within 28 days prior to C11-AMT PET imaging.

**C.** If both whole body PET scan and a CT scan with IV contrast (chest, abdomen, pelvis and neck if applicable) have been performed separately prior to study entry, this is acceptable as long as the whole body PET scan is within 28 days of C11-AMT PET imaging and the CT with IV contrast is within 28 days of starting pembrolizumab.

Following pembrolizumab infusions administered every 3 weeks x 4 cycles, antitumor response will be assessed at 12 weeks by performing a whole body FDG PET scan coregistered with CTIVC. As an alternative, CTIVC of the chest, abdomen, and pelvis (add neck, if applicable) is acceptable and can be used for this assessment of antitumor response by RECIST v1.1 criteria. It is quite possible that patients may progress earlier than 12 weeks; in this case, an evaluable patient will be a patient who has received at least two pembrolizumab infusions and subsequently had restaging scans to document radiographic progression and measurement by RECIST v1.1 criteria. Antitumor response will then be correlated with various C11-AMT PET parameters at baseline (e.g. SUVmax, total tumor metabolic volume, measurement of intra-tumoral and inter-lesion heterogeneity), which is the primary endpoint of the study. Toxicity will be assessed during treatment via NCI CTCAE v4.03. Following week 12, subjects will have completed study treatment requirements, and after discussion with their doctor they will be allowed to continue pembrolizumab per standard of care until disease progression or other reasons (e.g., unacceptable toxicity). Long-term follow up and treatment of all patients who continue to have clinical benefit from pembrolizumab (complete response, partial response, stable disease) will be maintained as per standard of care.

#### 4.2.1 Treatment Dosage and Administration

After screening and pretreatment, treatment will consist of the following:

Pembrolizumab 200mg IV flat dose will be administered over 30 minutes on Day 1; Pembrolizumab dosing will be repeated every 3 weeks until progression or subject withdrawal for other reasons.

Agent	Dose/Frequency	Route	Schedule
Pembrolizumab	200mg every 3 weeks	IV over 30 minutes	Starting on D1 of study; Every 3 weeks (21 days) until disease progression or withdrawal for other reasons

On-study treatment is 12 weeks of pembrolizumab.

#### 4.3 Toxicities and Dosing Delays/Dose Modifications

##### 4.3.1 Pembrolizumab Administration

Pembrolizumab 200 mg will be administered as a 30-minute IV infusion starting on Day 1 (D1) of the study (hematology labs must meet inclusion criteria to initiate therapy with pembrolizumab). Every effort should be made to target infusion timing to be as close to 30 minutes as possible. However, given the variability of infusion pumps from site to site, a window of -5 minutes and +10 minutes is permitted (i.e., infusion time is 30 minutes: -5 min/+10 min). The Pharmacy Manual contains specific instructions for the preparation of the pembrolizumab infusion fluid and administration of infusion solution. This manual is provided as a document separate from the protocol.

##### 4.3.1.1 Management of Infusion Reactions for Pembrolizumab

Signs and symptoms usually develop during or shortly after drug infusion and generally resolve completely within 24 hours of completion of infusion. Refer to the table below for infusion reaction treatment guidelines:

NCI CTCAE Grade	Treatment	Premedication at subsequent dosing
Grade 1 Mild reaction; infusion interruption not indicated; intervention not indicated	Increase monitoring of vital signs as medically indicated until the subject is deemed medically stable in the opinion of the investigator.	None
Grade 2 Requires infusion interruption but responds promptly to symptomatic treatment (e.g., antihistamines, NSAIDS, narcotics, IV fluids); prophylactic medications indicated for < =24 hrs	Stop Infusion and monitor symptoms. Additional appropriate medical therapy may include but is not limited to: IV fluids Antihistamines NSAIDS Acetaminophen Narcotics Increase monitoring of vital signs as medically indicated until the subject is deemed medically stable in the opinion of the investigator. If symptoms resolve within one hour of stopping drug infusion, the infusion may be restarted at 50% of the original infusion rate (e.g., from 100 mL/hr to 50 mL/hr). Otherwise dosing will be held until symptoms resolve and the subject should be premedicated for the next scheduled dose. Subjects who develop Grade 2 toxicity despite adequate premedication should be permanently discontinued from further trial treatment administration.	Subject may be premedicated 1.5h (± 30 minutes) prior to infusion of pembrolizumab (MK-3475) with:  Diphenhydramine 50 mg po (or equivalent dose of antihistamine).  Acetaminophen 500-1000 mg po (or equivalent dose of antipyretic).
Grades 3 or 4 Grade 3: Prolonged (i.e., not rapidly responsive to symptomatic medication and/or brief interruption of infusion); recurrence of symptoms following initial improvement; hospitalization indicated for other clinical sequelae (e.g., renal impairment, pulmonary infiltrates) Grade 4: Life-threatening; pressor or ventilatory support indicated	Stop Infusion. Additional appropriate medical therapy may include but is not limited to: IV fluids Antihistamines NSAIDS Acetaminophen Narcotics Oxygen Pressors Corticosteroids Epinephrine  Increase monitoring of vital signs as medically indicated until the subject is deemed medically stable in the opinion of the investigator. Hospitalization may be indicated. Subject is permanently discontinued from further trial treatment administration.	No subsequent dosing
Appropriate resuscitation equipment should be available in the room and a physician readily available during the period of drug administration.		

#### 4.3.1.2 Other Dose Modifications for Pembrolizumab

Adverse events (both non-serious and serious) associated with pembrolizumab exposure may represent an immunologic etiology. These adverse events may occur shortly after the first dose or several months after the last dose of treatment. Pembrolizumab must be withheld for drug-related toxicities and severe or life-threatening AEs as per Table below. Also see section 4.3.1.3 for supportive care guidelines, including use of corticosteroids.

Dosing interruptions are permitted in the case of medical/surgical events or logistical reasons not related to study therapy (e.g., elective surgery, unrelated

medical events, patient vacation, and/or holidays). Subjects should be placed back on study therapy within 3 weeks of the scheduled interruption, unless otherwise discussed with the Sponsor. The reason for interruption should be documented in the patient's study record.

If a dose of pembrolizumab is delayed, then the subsequent dose should be administered when symptoms have resolved to a level permissive for re-initiation of therapy.

**Dose Modification Guidelines for Pembrolizumab**

Toxicity	Hold Treatment For Grade	Timing for Restarting Treatment	Treatment Discontinuation
Diarrhea/Colitis	2-3	Toxicity resolves to Grade 0-1	Toxicity does not resolve within 12 weeks of last dose or inability to reduce corticosteroid to 10 mg or less of prednisone or equivalent per day within 12 weeks
	4	Permanently discontinue	Permanently discontinue
AST, ALT, or Increased Bilirubin	2	Toxicity resolves to Grade 0-1	Toxicity does not resolve within 12 weeks of last dose
	3-4	Permanently discontinue (see exception below) a	Permanently discontinue
Type 1 diabetes mellitus (if new onset) or Hyperglycemia	T1DM or 3-4	old pembrolizumab for new onset Type 1 diabetes mellitus or Grade 3-4 hyperglycemia associated with evidence of beta cell failure	Resume pembrolizumab when patients are clinically and metabolically stable
Hypophysitis	2-4	Toxicity resolves to Grade 0-1. Therapy with pembrolizumab can be continued while endocrine replacement therapy is instituted	Toxicity does not resolve within 12 weeks of last dose or inability to reduce corticosteroid to 10 mg or less of prednisone or equivalent per day within 12 weeks
Hyperthyroidism	3	Toxicity resolves to Grade 0-1	Toxicity does not resolve within 12 weeks of last dose or inability to reduce corticosteroid to 10 mg or less of prednisone or equivalent per day within 12 weeks
	4	Permanently discontinue	Permanently discontinue
Hypothyroidism	2	Therapy with pembrolizumab can be continued while thyroid replacement therapy is instituted	Therapy with pembrolizumab can be continued while thyroid replacement therapy is instituted
Infusion Reaction	2 b	Toxicity resolves to Grade 0-1	Permanently discontinue if toxicity develops despite adequate premedication
	3-4	Permanently discontinue	Permanently discontinue
Pneumonitis	2	Toxicity resolves to Grade 0-1	Toxicity does not resolve within 12 weeks of last dose or inability to reduce corticosteroid to 10 mg or less of prednisone or equivalent per day within 12 weeks
	3-4	Permanently discontinue	Permanently discontinue
Renal Failure or Nephritis	2	Toxicity resolves to Grade 0-1	Toxicity does not resolve within 12 weeks of last dose or inability to reduce corticosteroid to 10 mg or less of prednisone or equivalent per day within 12 weeks
	3-4	Permanently discontinue	Permanently discontinue
All Other Drug-Related Toxicity c	3 or Severe	Toxicity resolves to Grade 0-1	Toxicity does not resolve within 12 weeks of last dose or inability to reduce corticosteroid to 10 mg or less of prednisone or equivalent per day within 12 weeks
	4	Permanently discontinue	Permanently discontinue

**Note: Permanently discontinue for any severe or Grade 3 drug-related AE that recurs or any life-threatening event.**

1a For patients with liver metastasis who begin treatment with Grade 2 AST or ALT, if AST or ALT increases by greater than or equal to 50% relative to baseline and lasts for at least 1 week then patients should be discontinued.

2b If symptoms resolve within one hour of stopping drug infusion, the infusion may be restarted at 50% of the original infusion rate (e.g., from 100 mL/hr to 50 mL/hr). Otherwise dosing will be held until symptoms resolve and the subject should be premedicated for the next scheduled dose; Refer to 4.3.1.1 – Infusion Treatment Guidelines for further management details.

c Patients with intolerable or persistent Grade 2 drug-related AE may hold study medication at physician discretion. Permanently discontinue study drug for persistent Grade 2 adverse reactions for which treatment with study drug has been held, that do not recover to Grade 0-1 within 12 weeks of the last dose.

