### 4.3.1.3 Rescue Medications and Supportive Care for Pembrolizumab

#### Supportive Care Guidelines

Patients should receive appropriate supportive care measures as deemed necessary by the treating investigator. Suggested supportive care measures for the management of adverse events with potential immunologic etiology are outlined below. Where appropriate, these guidelines include the use of oral or intravenous treatment with corticosteroids as well as additional anti-inflammatory agents if symptoms do not improve with administration of corticosteroids. Note that several courses of steroid tapering may be necessary as symptoms may worsen when the steroid dose is decreased. For each disorder, attempts should be made to rule out other causes, such as metastatic disease or bacterial or viral infection, which might require additional supportive care. The treatment guidelines will be applied when the investigator determines the events to be related to pembrolizumab.

**Note:** if after the evaluation the event is determined not to be related, the investigator does not need to follow the treatment guidance (as outlined below). Refer to Section 4.3.1.2 for dose modifications.

It may be necessary to perform conditional procedures, such as bronchoscopy, endoscopy, or skin photography as part of evaluation of the event.

- **Pneumonitis:**
  - For **Grade 2 events**, treat with systemic corticosteroids. When symptoms improve to Grade 1 or less, steroid taper should be started and continued over no less than 4 weeks.
  - For **Grade 3-4 events**, immediately treat with intravenous steroids. Administer additional anti-inflammatory measures, as needed.
  - Add prophylactic antibiotics for opportunistic infections in the case of prolonged steroid administration.
  
- **Diarrhea/Colitis:**

Subjects should be carefully monitored for signs and symptoms of enterocolitis (such as diarrhea, abdominal pain, blood or mucus in stool, with or without fever) and of bowel perforation (such as peritoneal signs and ileus).

  - All subjects who experience diarrhea/colitis should be advised to drink liberal quantities of clear fluids. If sufficient oral fluid intake is not feasible, fluid and electrolytes should be substituted via IV infusion. For Grade 2 or higher diarrhea, consider GI consultation and endoscopy to confirm or rule out colitis.
  - For **Grade 2 diarrhea/colitis** administer oral corticosteroids.

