  - For **Grade 3-4** events, treat with intravenous corticosteroids for 24 to 48 hours.
  - When symptoms improve to Grade 1 or less, a steroid taper should be started and continued over no less than 4 weeks.
  
- **Renal Failure or Nephritis:**
  - For **Grade 2** events, treat with corticosteroids.
  - For **Grade 3-4** events, treat with systemic corticosteroids.
  - When symptoms improve to Grade 1 or less, steroid taper should be started and continued over no less than 4 weeks.
  
- **Steven's Johnson Syndrome (SJS) and Toxic Epidermal Necrolysis (TEN)**
  - For signs and symptoms of SJS or TEN, withhold pembrolizumab and refer the patient for specialized care for assessment and treatment
  - If SJS or TEN is confirmed, permanently discontinue pembrolizumab
  
- **Immune-mediated myocarditis management**
  - For suspected immune-mediated myocarditis, ensure adequate evaluation to exclude other etiologies and administer corticosteroids as appropriate
  
- **Infusion Reaction:**

See section 4.3.1.1

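### The note under the pembrolizumab dose-modification table ends treatment after any life-threatening event, but the hypophysitis and T1DM/hyperglycemia rows allow further dosing at Grade 4.

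*Combined protocol and SAP*

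**What the plan says.** Section 4.3.1.2 makes its table the governing text: "Pembrolizumab must be withheld for drug-related toxicities and severe or life-threatening AEs as per Table below". The note directly beneath the table adds an override: "Permanently discontinue for any severe or Grade 3 drug-related AE that recurs or any life-threatening event".

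Two rows cover Grade 4 without a separate Grade 4 line:

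- **Hypophysitis, Grades 2-4.** The restart cell reads "Toxicity resolves to Grade 0-1. Therapy with pembrolizumab can be continued while endocrine replacement therapy is instituted". Its discontinuation cell mentions only failure to resolve, or failure to reduce the corticosteroid dose, within 12 weeks.
- **New-onset T1DM or Grade 3-4 hyperglycemia.** The row applies to "Grade 3-4 hyperglycemia associated with evidence of beta cell failure" as well as to new-onset T1DM, and says "Resume pembrolizumab when patients are clinically and metabolically stable".

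The protocol puts Grade 4 into words in the infusion-reaction table of Section 4.3.1.1: "Life-threatening; pressor or ventilatory support indicated".

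Section 4.3.1.3, on supportive care, tells the reader "Refer to Section 4.3.1.2 for dose modifications". It also contains a dosing instruction of its own: "If SJS or TEN is confirmed, permanently discontinue pembrolizumab". The table in 4.3.1.2 has no SJS/TEN row.

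**The concern.** A site treating a patient with Grade 4 hypophysitis or Grade 4 hyperglycemia would look up the row and find a route back to treatment. It would then read the note and find that treatment has ended for good. The note states no exceptions, and neither row claims one. Elsewhere the table does mark an exception when it intends one: the AST/ALT/bilirubin row points to a footnote.

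At stake is whether a patient is re-exposed to the drug after a serious endocrine event. Affiliate sites take part, so different readers will apply the table, and Section 4.5 offers no tie-break beyond listing unacceptable adverse events as a reason to stop. The situation is foreseeable: Section 5.1.6 reports a Grade 4 hypophysitis with onset at 1.7 months, about 7.4 weeks (1.7 × 52/12), inside the 12 weeks of study treatment.

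**Working it through.** The plan has no figure to reproduce. The check sets each row, by grade, against the note and against Section 4.3.1.3.

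1. **Grade 4 hypophysitis.** Row: restart at Grade 0-1, or continue with replacement. Note: stop permanently if life-threatening. *Conflict, if Grade 4 is life-threatening.*
2. **Grade 4 hyperglycemia with beta cell failure.** Row: resume when stable. Note: stop permanently if life-threatening. *Conflict on the same condition.* New-onset T1DM is listed without a grade, so it conflicts only when the case is life-threatening.
3. **Grade 4 in the other rows that list it** (diarrhea/colitis, AST/ALT/bilirubin, hyperthyroidism, infusion reaction, pneumonitis, renal failure/nephritis, all other drug-related toxicity). Row and note both end treatment; the AST/ALT/bilirubin row adds its flagged exception. *No conflict.*
4. **First Grade 3 event** (diarrhea/colitis, hyperthyroidism, all other). Row: hold, then restart. The note acts on Grade 3 only if the event recurs. *No conflict; this half of the note adds to the table.*
5. **Hypophysitis row read alone.** Grades 2-4 stand in the hold column, while the next cell requires resolution to Grade 0-1 and also says therapy can be continued. *Ambiguous.*
6. **Hypothyroidism.** Grade 2 stands in the hold column, while both action cells say to continue. Grades 3-4 have no line, so a literal reader goes to the catch-all row. Section 4.3.1.3 groups Grades 2-4 together for hormone replacement, but that treats the event and is not a dosing rule. *Column mismatch at Grade 2; a gap at Grades 3-4.*
7. **Confirmed SJS/TEN.** Section 4.3.1.3: stop permanently. With no row of its own, a Grade 3 or severe case would fall literally under the catch-all, which allows restart at Grade 0-1. *Weak conflict, since the only text naming the event is explicit.*

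**How often.** Inputs: hypophysitis incidence 0.5% (Section 5.1.6) and 27 patients (Section 8.2). Expected cases of any grade = 0.005 × 27 = 0.135, about 0.14. The chance of at least one = 1 − 0.995^27 ≈ 0.13. Grade 4 alone would be less frequent. The incidence of T1DM or Grade 3-4 hyperglycemia is not given, so no count is attempted for that row.

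**The case against.** The strongest defence concerns the meaning of Grade 4. The life-threatening wording comes from the infusion-reaction table. The documents define Grade 4 for neither hypophysitis nor hyperglycemia and leave grading to CTCAE v4.03. The drafter may have meant the endocrine rows as specific exceptions, given that hormone deficits can be replaced. That is why the conclusion is conditional. It does not remove the conflict: no exception is stated, and every other row that lists Grade 4 ends treatment there, apart from the flagged hepatic exception.

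The hypophysitis cell can also be read in sequence: hold, restart at Grade 0-1, and do not let ongoing replacement bar dosing. That reading is fair, so the hold/continue wording is called ambiguous and kept secondary.

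Several stronger readings are tempting but unsupported:

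- **That re-exposure after confirmed SJS/TEN is an open choice.** A site would have to pass over the one sentence that names the event. If the case is life-threatening, the note gives the same answer. What stands is that Section 4.3.1.3 calls its measures suggested, sends the reader to 4.3.1.2, and finds no row there.
- **That hypothyroidism is a frequent restart-or-stop conflict.** The 8.3% in Section 5.1.6 is not broken down by grade. Section 1.3.2 gives 0.2% for Grade 3-4. Median onset is 3.5 months, about 15 weeks (3.5 × 52/12), after study treatment ends, and nobody is reported to have stopped pembrolizumab for it.
- **That the T1DM row has its texts in the wrong columns.** The cell is visibly damaged in the available text, so its layout proves nothing.
- **That exposure before the week-12 scan would shift.** About 0.14 expected hypophysitis cases cannot support this, and nothing in Section 8.2 depends on it.

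**Conclusion.** The concern holds in a narrow form. Grade 4 hypophysitis and Grade 4 hyperglycemia (and new-onset T1DM when life-threatening) each have a row that permits further dosing and a note that forbids it, with no stated precedence. This rests on one assumption: that Grade 4 carries for these events the life-threatening meaning that Section 4.3.1.1 gives it for infusion reactions. If the sponsor intends otherwise, the text needs to say so.

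The hypophysitis and hypothyroidism hold wording, the missing hypothyroidism grades and the missing SJS/TEN row are secondary points of clarity. They should not be counted as further conflicts of equal weight.

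The events are rare and there is no material effect on the analysis. The weight comes from the consequence for an individual patient: the two instructions differ between further dosing and none.

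**What to change.** The sponsor's medical lead should reconcile the Section 4.3.1.2 table and its note with Section 4.3.1.3, so that each event and grade carries one instruction:

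- Either make the note subject to named row exceptions, marked as the AST/ALT/bilirubin exception already is, or align the hypophysitis and T1DM/hyperglycemia rows with the note.
- State whether life-threatening in the note is to be read as Grade 4.
- Reword the hypophysitis row so that hold and continue cannot both apply at the same moment.
- Remove the Grade 2 hypothyroidism mismatch and list Grades 3-4 explicitly.
- Add an SJS/TEN cross-reference from the table to Section 4.3.1.3.

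Which instruction should stand is a clinical decision for the sponsor, and none is proposed here. The cost is one table edit in a protocol amendment, with no new procedures, patients or analyses.

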9. Has not received prior therapy with CTLA-4, PD-1/PD-L1 inhibitors, other co-stimulatory or co-inhibitory immune checkpoint antibody therapies (e.g. LAG3, TIM3, CD137, KIR3DL, CD70, and CD27) for distant metastatic melanoma. Patients who have received MAPK inhibitors are allowed on condition that they have recovered from adverse events to at most Grade 1 by CTCAE v4.03 and at least 15 days have elapsed between last dose of MAPK inhibitors and C11-AMT imaging. Patients who have previously received CTLA-4 inhibitors in the adjuvant setting are allowed to participate as long as they discontinued CTLA-4 treatment at least 30 days ago and meet criteria outlined in inclusion #14. Patients who have previously received adjuvant PD-1 inhibitors are excluded.
10. Demonstrate adequate organ function as defined in the table below; all screening labs to be obtained within 14 days prior to C11-AMT PET scan.

System	Laboratory Value
Hematological	
Hemoglobin (Hgb)	≥ 9 g/dL or ≥ 5.6 mmol/L without transfusion or EPO dependency (within 7 days of assessment of Hgb)
Absolute Neutrophil Count (ANC)	≥ 1,500/mm 
Platelets	≥ 100,000/mm 
Renal	
Serum Creatinine OR Measured or calculated creatinine clearance (GFR can also be used in place of creatinine or CrCl)	≤1.5 x ULN OR  ≥ 60 mL/min using the Cockcroft-Gault formula for subject with creatinine levels > 1.5 X institutional upper limits of normal (ULN)
Hepatic	
Serum Total Bilirubin	≤ 1.5 X ULN
Aspartate aminotransferase (AST)	≤ 2.5 X ULN OR < 5 X ULN for subjects with liver metastases

Alanine aminotransferase (ALT)	$\leq 2.5 \times \text{ULN}$ OR $< 5 \times \text{ULN}$ for subjects with liver metastases
Albumin	$\geq 2.5 \text{ mg/dL}$
Coagulation	
International Normalized Ratio (INR) or Prothrombin Time (PT)	$\leq 1.5 \times \text{ULN}$ , unless subject is receiving anticoagulant therapy as long as PT or PTT is within therapeutic range of intended use of anticoagulants
Activated Partial Thromboplastin Time (aPTT)	$\leq 1.5 \times \text{ULN}$ , unless subject is receiving anticoagulant therapy as long as PT or PTT is within therapeutic range of intended use of anticoagulants

11. Female subjects of childbearing potential should have a negative urine or serum pregnancy within 14 days prior to C11-AMT PET scan. If the urine test is positive or cannot be confirmed as negative, a serum pregnancy test will be required.

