  - For **Grade 3 or 4 diarrhea/colitis**, treat with intravenous steroids followed by high dose oral steroids.

- When symptoms improve to Grade 1 or less, steroid taper should be started and continued over no less than 4 weeks.
- **Type 1 diabetes mellitus (if new onset, including diabetic ketoacidosis [DKA]) or  $\geq$  Grade 3 Hyperglycemia, if associated with ketosis (ketonuria) or metabolic acidosis (DKA)**
  - For **T1DM** or **Grade 3-4** Hyperglycemia
    - Insulin replacement therapy is recommended for Type I diabetes mellitus and for Grade 3-4 hyperglycemia associated with metabolic acidosis or ketonuria.
    - Evaluate patients with serum glucose and a metabolic panel, urine ketones, glycosylated hemoglobin, and C-peptide.
- **Hypophysitis:**
  - For **Grade 2** events, treat with corticosteroids. When symptoms improve to Grade 1 or less, steroid taper should be started and continued over no less than 4 weeks. Replacement of appropriate hormones may be required as the steroid dose is tapered.
  - For **Grade 3-4** events, treat with an initial dose of IV corticosteroids followed by oral corticosteroids. When symptoms improve to Grade 1 or less, steroid taper should be started and continued over no less than 4 weeks. Replacement of appropriate hormones may be required as the steroid dose is tapered.
- **Hyperthyroidism or Hypothyroidism:**

Thyroid disorders can occur at any time during treatment. Patients should be monitored for changes in thyroid function (at the start of treatment, periodically during treatment, and as indicated based on clinical evaluation) and for clinical signs and symptoms of thyroid disorders.

  - **Grade 2** hyperthyroidism events (and **Grade 2-4** hypothyroidism):
    - In hyperthyroidism, non-selective beta-blockers (e.g. propranolol) are suggested as initial therapy.
    - In hypothyroidism, thyroid hormone replacement therapy, with levothyroxine or liothyronine, is indicated per standard of care.
  - **Grade 3-4** hyperthyroidism
    - Treat with an initial dose of IV corticosteroid followed by oral corticosteroids. When symptoms improve to Grade 1 or less, steroid taper should be started and continued over no less than 4 weeks. Replacement of appropriate hormones may be required as the steroid dose is tapered.

- **Hepatic:**
  - For **Grade 2** events, monitor liver function tests more frequently until returned to baseline values (consider weekly).
    - Treat with IV or oral corticosteroids

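### For liver-metastasis patients who start at Grade 2 AST/ALT, the hold, restart and discontinuation passages conflict and need to be reconciled

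*Combined protocol and SAP*

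**What the plan says.** Criterion 10 in section 3.1 sets the AST and ALT limits for entry and relaxes both to "< 5 X ULN for subjects with liver metastases".

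Section 4.3.1.2 states the scope of the dose table: "Pembrolizumab must be withheld for drug-related toxicities and severe or life-threatening AEs as per Table below". The row headed "AST, ALT, or Increased Bilirubin" has two lines:

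- **Grade 2:** hold. The restart cell reads "Toxicity resolves to Grade 0-1" and the discontinuation cell reads "Toxicity does not resolve within 12 weeks of last dose". Neither carries a footnote marker or refers to the patient's baseline.
- **Grade 3-4:** the restart cell reads "Permanently discontinue (see exception below" and carries marker a. The discontinuation cell calls for permanent discontinuation, with no marker.

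Footnote a opens "For patients with liver metastasis who begin treatment with Grade 2 AST or ALT". It discontinues such patients if AST or ALT rises by 50% or more over baseline and the rise lasts a week or longer. It names no grade for the risen value and gives no action for a smaller or shorter rise.

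The hepatic paragraph of section 4.3.1.3 says, for Grade 2 events, to "monitor liver function tests more frequently until returned to baseline values (consider weekly"). It starts the steroid taper once improvement reaches Grade 1 or less. The Time and Events Table (section 6.1) schedules liver function tests at screening, on day 1 of each of the four cycles and at end of treatment. Section 4.2.1 sets the cycle at 21 days.

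**The concern.** The protocol knowingly admits patients whose AST or ALT is already Grade 2, but its Grade 2 rule is written as if every patient began at Grade 0-1. The one provision that looks at the patient's own baseline is attached to the Grade 3-4 line, and its wording does not match that position. Two investigators with the same laboratory values could reach different decisions on holding, restarting or stopping pembrolizumab, and each could cite the protocol. That bears on patient safety and on who continues treatment.

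**Working it through.** The plan gives no figure to reproduce. The check sets the passages side by side and uses simple arithmetic to find where they diverge.

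**Inputs.** From the documents: entry limit below 5 x ULN; restart at Grade 0-1; discontinuation limit of 12 weeks from last dose; footnote trigger of a 50% rise lasting 1 week; 21-day cycles. Assumed, because the documents cite CTCAE v4.03 but print no cut-offs: Grade 3 begins above 5 x ULN, and Grade 2 begins above L, with L between 2.5 and 3.0 x ULN. Let B be the baseline in multiples of ULN, so for this subgroup L < B < 5.

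**Step 1. Return to baseline does not permit restart.** After a hold, the value must fall to L or below. The required fall below the patient's own baseline is 1 - L/B.

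- B = 4.5: 1 - 3.0/4.5 = 33% to 1 - 2.5/4.5 = 44%.
- B = 3.2: 1 - 3.0/3.2 = 6% to 1 - 2.5/3.2 = 22%.

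For example, a drug-related rise from 4.5 to 4.9 (4.9/4.5 = +9%) stays Grade 2 and triggers the hold. If the value settles back at 4.5, it is still Grade 2, restart is barred, and the 12-week limit then requires discontinuation. This step needs no assumption about cut-offs: a Grade 2 baseline is by definition not Grade 0-1.

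**Step 2. Footnote a against the Grade 2 row.** A 50% rise stays within Grade 2 when 1.5 x B is at most 5, that is, B is at most 5/1.5 = 3.33. Such baselines exist under either value of L (1.5 x 2.5 = 3.75; 1.5 x 3.0 = 4.5; both below 5). For example, B = 3.2 gives 1.5 x 3.2 = 4.8, still Grade 2. If this lasts a week, footnote a says discontinue while the Grade 2 row says hold and wait up to 12 weeks.

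**Step 3. Grade 3 values below the trigger.** When B exceeds 3.33, Grade 3 can be reached with a rise under 50%. For example, B = 4.5 has its trigger at 1.5 x 4.5 = 6.75, and a rise to 6.0 is 6.0/4.5 = +33%. The restart cell sends the reader to the exception, the discontinuation cell says to stop permanently, and the footnote is silent. The same ambiguity applies to a Grade 3 rise of 50% or more that lasts under a week.

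**Step 4. Persistence.** The trigger turns on 7 days, but scheduled liver tests are 21 days apart. A rise found on day 1 of a cycle has no scheduled retest near day 8. More frequent testing, with weekly as a suggestion, is mentioned only for Grade 2 hepatic events.

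**The case against.** The case for leaving the text alone has several sound parts.

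- **Scope.** The table governs drug-related toxicity, and section 4.3.1.3 asks for metastatic disease to be ruled out as a cause. An unchanged Grade 2 baseline from liver metastases therefore does not clearly trigger a hold. This stands, and it limits the point to rises judged drug-related.
- **Monitoring target.** Return to baseline in the hepatic paragraph says how long to monitor; it is not a restart rule, and that section refers dose modification back to 4.3.1.2. This stands. The paragraph needs aligning, but the contradiction does not rest on it.
- **Unscheduled tests.** Section 7.3.3.1 recognises unscheduled laboratory testing, so persistence could be shown. It could, but no passage requires such a test or names it for footnote a.

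A reader might also infer more than the documents support:

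- **That milder rises are in general treated more strictly than larger ones.** A sustained rise of 50% or more means discontinuation, which is stricter than the Grade 2 hold. The order could reverse only for Grade 3 values under 50% above baseline or lasting under a week, and only if the footnote's silence is read as permission to continue.
- **That no hold or stop applies to those Grade 3 values.** The unmarked discontinuation cell says otherwise, and the note above the footnotes separately covers recurrent Grade 3 and life-threatening events.
- **That patients would be held without limit.** The Grade 2 row ends the hold at 12 weeks from the last dose.
- **That liver-metastasis patients would be lost selectively from the primary analysis.** Only section 6.7 requires two doses for evaluability without qualification; sections 4.2 and 8.1 tie that condition to progression before week 12. A patient held after dose 1 might also improve to Grade 0-1. The number entering at Grade 2 is not given.

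**Conclusion.** The conflict is real and confined to patients with liver metastases who begin at Grade 2 AST or ALT and then have a rise judged drug-related. It has three parts: a full return to baseline cannot lead to restart (Step 1); footnote a and the Grade 2 row give different actions for a sustained 50% rise that remains Grade 2 (Step 2); and the action for a Grade 3 value below the footnote's trigger is unclear (Step 3). The persistence condition also lacks a test to establish it.

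The first part follows from the text alone. The 3.33 x ULN dividing line and the examples in the other two rest on the assumed 5 x ULN boundary. The share of the 27 planned patients concerned cannot be derived, and no effect on power or on the primary comparison is shown. At most, a patient who never reaches a second dose would fail the evaluability condition in section 6.7. The point deserves correction because it is a stated rule conflict about continuing treatment. Which rule is clinically right is not judged here.

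**What to change.** Reconcile five places so that one consistent rule for hold, restart and discontinuation applies to patients who begin at Grade 2: the Grade 2 AST/ALT line, both cells of the Grade 3-4 line, footnote a, criterion 10, and the hepatic paragraph of section 4.3.1.3. The sponsor's clinical team should choose the rule. The revised text should say whether footnote a applies to rises that remain Grade 2, and what happens to a Grade 3 value that does not meet its trigger. It should also name the repeat liver function test that establishes 1-week persistence and add it to section 6.1.

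The cost is an amendment to wording plus one conditional laboratory test in the schedule. Sample size and analysis are unchanged.
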